Study 2: Our clinical study is a longitudinal randomized (6 month) cross over controlled clinical trial (RCT) intervention with two parallel arms (ratio: 1:1) with care-as-usual plus care coordination intervention. The purpose of Phase-II clinical trial is to examine effectiveness of the Care4AD platform to improve care coordination and caregivers burden and stress. For the purpose of this study, we will recruit 100 men and women older adults (Age 18+) persons with mild or moderate dementia/memory loss. Including self-reported memory loss and MOCA score of 26 or lower.

Both groups will receive identical Care4AD platform (tablet). However, all feedbacks (e.g., reminder about completed/incomplete tasks) will be activated in the intervention group (IG) and the caregiver will have companion app downloaded on their smartphone. Reminder notifications will be de-activated in the control group (CG) and no app will be supplied. CG will receive conventional care coordination intervention through bi-weekly interview and will be provided with

7/25/24, 1:58 PM Human Protocol Report
scheduled care tasks similar to IG. Participants will be informed that the purpose of this program is to examine effectiveness of a care coordination program to reduce stress and burden of care givers and improve adherence to scheduled care tasks and improve mobility. The type of intervention will not be disclosed to participants at baseline (blinded study design) as both groups will receive some sort of care coordination intervention. In addition, the person who will analyze the data will be blinded to the type of intervention. At the 3 month visit, participants will be crossed over to either intervention or control and follow procedures.

Inclusion Criteria:

Male and female older patients (> 18 years old) with mild or moderate memory loss, self- reported memory loss, or MOCA score 26 or lower, and who are ambulatory and are in a residential home with a caregiver/informant or in a nursing home.

Caregivers and Health Professionals will be included in the subject population.

Exclusion Criteria:

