Spontaneous daily physical activity monitoring : Daily mobility performance and inactivity will be objectively monitored using a validated wearable technology named PAMSys, a sensor that can be worn as a pendant around the neck. We will assess multiple parameters such as number of taken steps, longest walking bout, standing duration, sedentary behavior, etc. Subjects will be monitored for up to 1 week continuously at baseline and at the end of the study. Subjects will be provided with a prepaid fedex envelop to return the Pamsys device to the research team.

Upper Extremity Test: Investigators will measure arm motion from each participant by implementing a validated technology based on wearable sensor system named LegSys. This system will assess respectively spatio-temporal parameters of arm motion as well as gait in a clinical setting. The LegSys system will be used with one sensor to capture arm motion, the sensor will be placed at the subject's wrist. While being at a comfortable position, the subject will be asked to flex and extend their arm for 20 seconds at a fast speed. Subject will also be asked to repeat this task but counting backwards as they flex and extend their arm (dual task).

Photos and media: We will be asking permission of the subject to take photos, film videos and/or record audio during the visits.

Care4AD: The research coordinator will provide the platform and explain to the subject and their caregiver how to interact with it. Together they will set up a schedule of regular IADL to follow. Intervention group will receive reminder notifications on their tablet to complete tasks and caregivers will be able to edit tasks on companion app downloaded on their smartphone. Control group will not receive reminder notifications and caregiver companion app will not be given.

Phone calls: Research Coordinators will call subjects bi-weekly to assess compliance to IADL schedule set up on the Care4AD platform. During the phone call, the coordinator will ask questions regarding acceptability and perceived usefulness and benefit of the platform. They may also call the subject for study related questions and to assess of there have been no adverse events (falls, hospitalization, etc).

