At the 3 month visit, the following procedures will be completed: Questionnaires, Gait, Balance, Motor-Cognitive Exercise program, Spontaneous physical activity monitoring, Upper Extremity Test, Photos and Media. Crossover will also happen, intervention group will become controls and controls will become part of the intervention group.

At 6 months, the following procedures will be completed: Questionnaires, Gait, Balance, Spontaneous physical activity monitoring, Upper Extremity Test, Photos and Media. At the end of the visit, the subject will return the platform to the research team.

Section G: Sample Size/Data Analysis

G1. Sample Size

How many subjects (or specimens, or charts) will be used in this study?

Local: 130 Worldwide: 130

Please indicate why you chose the sample size proposed:

Phase I: N=30 total subjects including 10 eligible Individuals With Dementia, at least one of the caregivers (n=10), and 10 expert clinicians unaffiliated with this project, who are providing care for Individuals With Dementia and their caregivers. The sample size for Phase I is chosen based on our experience with assessing technologies for older populations and also considering the timeline and budget limitation for Phase I. Over the past decade, we have evaluated the usability of a number of such technologies and we have found that the proposed sample size is adequate for identifying potential shortcomings that might require design or implementation modifications.

Phase II: N=100 total subjects, Individuals With care-givers, age 18+, who are supporting an individual with memory loss, aged 50+, male and female, who satisfied inclusion and exclusion criteria described in the following. The required sample size for Phase II was calculated based on our primary endpoints: 1) reduce burden for the caregivers in the Intervention group, 2) better adherence in the Intervention group compared to control group, and 3) change in functional performance over 6 month.

G2. Data Analysis

Provide a description of your plan for data analysis. State the types of comparisons you plan (e.g. comparison of means, comparison of proportions, regressions, analysis of variance). Which is the PRIMARY comparison/analysis? How will the analyses proposed relate to the primary purposes of your study?

7/25/24, 1:58 PM Human Protocol Report

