Study 2: Results of the user experience questionnaires will be calculated as median (range) for each Likert-scale question. Unpaired t-tests, Mann-Whitney u-tests, and Chi-square will be used for baseline between groups comparison to verify effectiveness of randomization. Linear mixed models will be used to test the effect of the Care4AD care coordination intervention on caregiver burden/stress at 6 months compared to baseline and between groups. Mixed models that accommodate the longitudinal design, allow for testing differences between groups in patterns over time, as well as at specific time points are consistent with an intention to treat analysis, and are valid for data which are missing at random. Appropriate mixed models (linear for continuous or Generalized Estimating Equations (GEEs) for non-continuous or non-parametric variables) will be used to test the intervention effect for each of the secondary outcomes (depression, cognitive function, QoL, fear of falls, neurotic tendency including fatigue, physical activity, adverse events, missing appointments). Univariate linear regression analyses will be performed to delineate predictive factors of training response for the primary study endpoint (pre- to post- changes in care coordination outcomes). Baseline values include age, gender, BMI, fear of falling, ADL-status, comorbidity, cognitive performance, depression, stage of AD, and baseline motor variables (e.g., balance and gait speed). We will use Spearman correlation coefficient to compare changes in quantitative metrics of exercise performance over the course of the program with in clinic assessments of functional performance (e.g., gait speed) and cognitive performance (e.g., MoCA). We will assess the agreement between Care4AD derived ADL, the Katz Index, and the Lawton-ADL. To demonstrate the acceptability of Care4AD application, we will use TAM model described above using 5-point Likert response questions. For all assessments, a p-value of 0.050 or less will be considered as statistically significant level. To evaluate the effect of sex as biological variable, we will examine whether acceptability and benefits of Care4AD platform to improve care coordination outcomes (between groups as well as compared to baseline) are different between men and women.

Section H: Potential Risks/Discomforts

H1. Potential Risks/Discomforts

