H3. Coordination of information among sites for multi-site research

Is the BCM Principal Investigator acting as the SPONSOR-INVESTIGATOR for this multi-site research?

No or Not Applicable

Is BCM the COORDINATING CENTER for this multi-site research?

Section I: Potential Benefits

Describe potential benefit(s) to be gained by the individual subject as a result of participating in the planned work.

The main benefit to subjects is the positive feeling that they will have by participating in a study that will potentially help other people by developing new technology that could improve the care of dementia and older adults and could assist in coordinating care, reducing burden and stress of caregivers, as well as improving safety and autonomy of individuals with dementia. They might eventually directly benefit from this technology if the device became validated and available for clinical use in the future. In addition, during the study all participants will receive care coordination intervention, which have been shown to be effective in reducing stress and burden of caregivers, which showed to be effective in improving balance and mobility in people with dementia. The subjects will be compensated for their time (\$50 for Phase I, and \$100 per month for the Phase II). Except baseline screening, no other visits to the clinic is needed for the intervention group.

Describe potential benefit(s) to society of the planned work.

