Please describe the methods of transmission of any research data (including PHI, sensitive, and non-sensitive data) to sponsors and/or collaborators.

Transmissions, if any, will only happen via secure emails.

Will you obtain a Certificate of Confidentiality for this study?

No

Please further discuss any potential confidentiality issues related to this study.

There are no further confidentiality issues related to this study.

Section L: Cost/Payment

Delineate clinical procedures from research procedures. Will subject's insurance (or subject) be responsible for research related costs? If so state for which items subject's insurance (or subject) will be responsible (surgery, device, drugs, etc). If appropriate, discuss the availability of financial counseling.

Delineate clinical procedures from research procedures. Will subject's insurance (or subject) be responsible for research related costs? If so state for which items subject's insurance (or subject) will be responsible (surgery, device, drugs, etc). If appropriate, discuss the availability of financial counseling. There will be no cost to the subject for all procedures. If subjects will be paid (money, gift certificates, coupons, etc.) to participate in this research project, please note the total dollar amount (or dollar value amount) and distribution plan (one payment, pro-rated payment, paid upon completion, etc) of the payment.

7/25/24, If subjects will be paid (money, gift certificates, coupons, etc.) to participate in this research project, please note the total dollar amount (or dollar value amount) and distribution plan (one payment, pro-rated payment, paid upon completion, etc) of the payment.

Dollar Amount:

350

Distribution Plan:

The subjects will be compensated for their time \$50 (one time) for Phase I.

Phase II: 3 visits - baseline, 3 month follow up, and 6 month follow, each visit 100\$ total for 300\$.

Note: Study 2 is NOT the continuation of Study 1. Subjects who participate in Study 1 may become eligible to participate in Study 2 only when they have met inclusion criteria. Please refer to inclusion/exclusion criteria.

Subjects will be given a ClinCard where payments will be loaded after a study visit or monthly phone call are completed. Additional information will be provided to the subject about how to manage the card.

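### Adverse events are a tested secondary outcome, but follow-up has no mandatory, standardised, dated enquiry about them

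*Combined protocol and SAP*

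**What the plan says.** **Analysis (G2, Study 2).** Mixed models or GEEs are to test the intervention effect on the "secondary outcomes (depression, cognitive function, QoL, fear of falls, neurotic tendency including fatigue, physical activity, adverse events, missing appointments").

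**Calls (F2, Study 2).** Two phone-call items appear. The first says that coordinators will call with health-related questions; it gives no frequency and names no adverse events. The second sets a regular call with a stated purpose: "Research Coordinators will call subjects bi-weekly to assess compliance to IADL schedule set up on the Care4AD platform". During that call the coordinator is to ask about acceptability and perceived usefulness. The item then adds: "They may also call the subject for study related questions and to assess of there have been no adverse events (falls, hospitalization, etc").

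**Visits (F2, Study 2).** Falls and hospitalisation history are recorded under Medical History at baseline. For the last visit the plan says: "At 6 months, the following procedures will be completed: Questionnaires, Gait, Balance, Spontaneous physical activity monitoring, Upper Extremity Test, Photos and Media". The 3-month list has these items too, plus an exercise programme and the crossover. Neither list repeats Medical History or adds an event review.

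**Call frequency (Section L).** The payment text says that "payments will be loaded after a study visit or monthly phone call are completed", which does not match bi-weekly calls.

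**Masking (F1).** Participants are not told the type of intervention at baseline, and the data analyst is masked. Nothing is said about coordinators.

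**The concern.** An outcome compared between conditions has to be sought in the same way, and equally often, in each. Here the duties that F2 states firmly for the regular call are schedule compliance and acceptability. The adverse-event enquiry is left to discretion. The coordinators who would exercise it also set up the platform and ask how useful it is, so they could readily learn which condition is running.

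The crossover adds a second difficulty. No event date or recall window is requested. A fall first reported at a call after the 3-month switch could have happened with or without reminders, and the record would not show which.

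At stake is the interpretation of one secondary comparison and of the trial's event reporting. A difference in capture between conditions would look like an effect of the platform, in either direction. Equal under-capture would not create a false difference, but it would cost precision. Events not asked about at the time are hard to recover later, particularly from people with memory loss.

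**Working it through.** The plan states no event rate, capture rate or power for adverse events, so there is no figure to reproduce. The check has two parts.

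**1. Where could an event be recorded after baseline?**

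| Contact | Required? | Names adverse events? | Schedule | Asks for a date? |
|---|---|---|---|---|
| Health-related call (F2) | Yes | No | None given | No |
| Compliance and acceptability call (F2) | Yes | Not in its stated content | Bi-weekly | No |
| Adverse-event enquiry (F2, same item) | Permissive | Yes | None given | No |
| 3-month visit (F2) | Yes | No | Once | No |
| 6-month visit (F2) | Yes | No | Once | No |

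No row is at once required, explicit about adverse events, scheduled and dated. The Questionnaires item does not clearly fill the gap: the instruments named include a fear-of-falling scale, but none is said to count falls or admissions.

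**2. What could uneven capture do? (assumed figures)**

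Let the true 3-month risk of any event be *p* in both conditions, and let a share *s* of events be captured. The observed risk is *p·s*, so the apparent ratio is s₂/s₁ whatever *p* is:

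- 90% versus 70%: 0.70/0.90 = 0.78
- 95% versus 85%: 0.85/0.95 = 0.89
- 90% versus 50%: 0.50/0.90 = 0.56

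For the chance of declaring a difference, take the first period only, 50 per group (100 randomised 1:1, no dropout) and two-sided alpha 0.05. G2 gives 0.050 without stating sidedness. The normal approximation, counting rejections in the direction of the bias, is

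Φ{ [ |p₁−p₂| − 1.96·√(2p̄(1−p̄)/n) ] / √( p₁(1−p₁)/n + p₂(1−p₂)/n ) }.

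Example with *p* = 20% and capture 90% versus 70%: p₁ = 0.18, p₂ = 0.14, p̄ = 0.16, n = 50. This gives (0.04 − 1.96 × 0.0733)/0.0732 = −1.42, and Φ = 0.078.

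| True risk in both groups | 90% v 70% capture | 90% v 50% capture |
|---|---|---|
| 20% | 7.8% | 20.8% |
| 30% | 10.4% | 31.1% |
| 40% | 13.4% | 42.8% |

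With equal capture the rate stays at the nominal 5%.

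Equal under-capture lowers power instead. For a true risk ratio of 0.5 and control risks of 20%, 30% and 40%, power is 29%, 43% and 59% at full capture. At 50% capture it is 16%, 22% and 29%.

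**The case against.** The strongest reply is that this is a minimal-risk pilot, that adverse events are one of eight listed secondary outcomes, and that the objectives concern care coordination, adherence and caregiver burden. No safety or fall-reduction claim is stated as an aim. That is right, and it limits the weight of the point. It does not remove the problem, because G2 does commit to testing this outcome.

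A reader might also infer several stronger things that the documents do not support:

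- *That the permissive sentence is the only route to an event.* The health-related call in F2 is not optional and could bring events to light. Section K also says that research data include health-record information, although no follow-up chart review is described. Neither is a defined adverse-event enquiry.
- *That the regular call excludes adverse events.* The sentence stands in the same item as the bi-weekly call and may mean extra calls on top of routine questioning. The text is ambiguous; it does not require the question, but it does not rule it out.
- *That events will be missed and compared unevenly.* No section sets a different enquiry by arm, and the calls go to subjects in general. Two statements make unequal contact plausible: F1 says "CG will receive conventional care coordination intervention through bi-weekly interview", and Section I says "Except baseline screening, no other visits to the clinic is needed for the intervention group", which conflicts with the three visits in F2 and Section L. Plausible is as far as this goes.
- *That participants will be asked a leading question.* The phrase about there having been no events is garbled form prose. No call script is given.
- *That the enquiry is halved.* Over 26 weeks, calls every two weeks give 26/2 = 13 contacts and monthly calls give 6. But the monthly figure comes from a payment clause that does not mention adverse events, so the contrast does not measure how often they are asked about.
- *That events just before a visit are never asked about.* A later call can pick up those before month 3. Only the last gap before month 6 has no later call, and at two-week intervals it is short.

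**Conclusion.** The point holds as a gap in the collection plan. A tested secondary outcome has no follow-up enquiry that is mandatory, standardised and dated, and discretion rests with staff not stated to be masked, across a switch of condition at 3 months. Under-capture, uneven capture and misplacement of events by period are risks; the documents do not show that any of them will occur.

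The size is unknown. Under an assumed 90% versus 70% capture and no true effect, the apparent ratio is 0.78. With an assumed 20% to 40% risk and 50 per group, a false difference would be declared in about 8% to 13% of trials. With equal capture there is no excess. The primary analysis is not affected. This is a cheap improvement.

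**What to change.** - In the F2 phone-call item, replace the permissive sentence with a fixed, neutrally worded question at every scheduled call in both conditions: any fall, hospitalisation or other health event since the last contact, with its date.
- Add the same question to the 3-month list, asked before the switch, and to the 6-month list.
- State in G2 that each event is analysed under the condition in force on its date.
- Reconcile the bi-weekly call in F2 with the monthly call in Section L.

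The cost is protocol wording and one short form in REDCap, which the study already uses for questionnaires. The calls and visits are already planned. The downside is a few minutes per contact and a higher recorded event count, which should be expected and not read as a safety signal in itself.

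### G1 gives no comparator for the burden and functional endpoints and G2 does not say which burden contrast decides, so a fall from baseline could count as success when the reminders and app add nothing

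*Combined protocol and SAP*

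**What the plan says.** - **G1 (Sample Size, Phase II)** says the sample size rests on three primary endpoints. The first is to "reduce burden for the caregivers in the Intervention group". The second is "better adherence in the Intervention group compared to control group". The third is "change in functional performance over 6 month". Only the second names a comparator.
- **G2 (Data Analysis, Study 2)** applies linear mixed models to burden and stress, tested "on caregiver burden/stress at 6 months compared to baseline and between groups". The G2 prompt asks which comparison is primary, and the Study 2 text does not answer it. The regression of predictive factors refers to the "primary study endpoint (pre- to post- changes in care coordination outcomes"), again without a comparator. The analysis by sex pairs between-group and from-baseline comparisons in the same way. One significance threshold, p of 0.050 or less, covers all assessments.
- **F1 (Design)** says "CG will receive conventional care coordination intervention through bi-weekly interview" and that controls get scheduled care tasks similar to those of the intervention group.
- **F2 (Procedure, Study 2)** describes a joint scheduling session and bi-weekly coordinator calls without limiting either to one arm. The arms swap at 3 months.
- **Section I (Potential Benefits)** says "all participants will receive care coordination intervention, which have been shown to be effective in reducing stress and burden of caregivers".
- **Section D** sets the objective: a randomized controlled evaluation of whether using Care4AD reduces caregiver burden and stress, among other aims.

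**The concern.** What separates the two conditions is the reminders and the caregiver app. Both include scheduled tasks, regular coordinator contact and some form of care coordination. If that common care lowers burden, or if scores drift down through regression to the mean, burden falls in the intervention group whether or not the reminders and app do anything. The control condition is there to remove this.

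G1's burden endpoint, read literally, does not use the control condition. G2 provides both a from-baseline and a between-group test, each at 0.050, with no order between them. An analyst following the text could report a significant fall from baseline as meeting the primary burden endpoint even if the between-group difference were null. At stake is whether the main efficacy claim can be attributed to Care4AD. Moving the assessment to 3 months would not cure this alone, because a one-arm change from baseline is uninformative at either visit.

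**Working it through.** **1. The plan's own figure.** G1 gives N = 100 and says it was calculated from the primary endpoints, but states no effect size, SD, power or dropout. It can be neither reproduced nor refuted. For orientation only, the detectable parallel-group difference with 50 per arm at two-sided 0.05 is

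d = (z₀.₉₇₅ + z_power) × √(2/50)

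- 80% power: (1.960 + 0.842) × 0.2 = 0.56 SD
- 90% power: (1.960 + 1.282) × 0.2 = 0.65 SD

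**2. Inputs for the check**

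| Input | Value | Source |
|---|---|---|
| Caregivers per arm | 50 | 100 (G1) at 1:1 (F1), taking one caregiver per randomized pair |
| Significance level | 0.05 | G2; two-sided is an assumption, as sidedness is not stated |
| Care4AD effect over control | 0 | Scenario under test |
| Shared improvement d, in SDs of the change score | 0.1 to 0.5 | Assumption; no Zarit effect or SD is given |

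**3. Test against baseline within one arm.** With n = 50, the paired t statistic has 49 degrees of freedom, critical value 2.010 and noncentrality d√50. The probability of significance is P(|t| > 2.010).

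| d | d√50 | Significant, two-sided | Significant reduction only |
|---|---|---|---|
| 0.1 | 0.707 | 10.7% | 10.3% |
| 0.2 | 1.414 | 28.4% | 28.3% |
| 0.3 | 2.121 | 54.8% | 54.8% |
| 0.4 | 2.828 | 79.2% | 79.2% |
| 0.5 | 3.536 | 93.4% | 93.4% |

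With no shared improvement (d = 0) the two columns are 5% and 2.5%.

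**4. Test between conditions.** The shared improvement cancels in the difference between arms, so the test keeps its nominal 5% (about 2.5% in favour of Care4AD) for every d. A simulation of 40,000 trials per value of d, with both arms of 50 improving equally, gave 4.9% to 5.2%.

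**5. Crossover.** At 6 months the arm first assigned to the intervention is in the control condition, and both sequences have had Care4AD. The burden of the intervention group at 6 months against baseline therefore does not isolate Care4AD either, and a sound between-condition contrast has to name its period or periods.

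**The case against.** The strongest reply is that G1 is shorthand in a sample-size rationale. Section D sets a randomized comparison as the objective, F1 describes a control group, and G2 plans a between-group test of burden and says the mixed models can test group differences over time. The G2 phrase can be read as change from baseline compared between groups. This stands in part. A reader might infer that the plan has settled on a within-group definition of success, and the documents do not support that. What remains is that G1 omits the comparator and G2 does not name the deciding contrast.

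A reader might also infer that the protocol itself predicts a fall in burden without the reminders and app. Section I does not go that far: it can mean that each arm gets its own form of care coordination, since F1 assigns the conventional bi-weekly interview to the control group and G2 calls Care4AD a care coordination intervention. The F2 calls are described as checking compliance, acceptability and adverse events. A shared effect is plausible on the protocol's account but is not stated as an expectation.

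Nor are participants told that the programme works. F1 says they are told its effectiveness is being examined, so a strong expectation effect cannot be read from the text.

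Finally, the study is classed as a pilot, the data for the right comparison are already planned, and the remedy is wording. That bears on severity and does not remove the defect.

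**Conclusion.** The concern holds in a limited form. G1 states burden and functional performance without a comparator, and G2 tests burden in two ways without saying which one counts. Following the text, a change from baseline could be reported as success on burden when the reminders and app add nothing.

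If judged on change from baseline, the chance of a significant result with no Care4AD effect is about 11%, 28%, 55% or 93% for shared improvements of 0.1, 0.2, 0.3 or 0.5 SD. If judged between conditions it is 5%. These figures assume 50 caregivers in the arm, two-sided testing and no loss to follow-up; the size of any shared improvement is unknown and may be zero, when the excess disappears. They describe a misuse that the wording permits, not the error rate of an analysis the plan has committed to.

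Severity: should-fix.

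**What to change.** - **G1:** state endpoints 1 and 3 in the form of endpoint 2, as the difference in Zarit Burden Interview score, and in functional performance, between the reminders-and-app condition and the control condition.
- **G2:** name that between-condition contrast as primary and say how the crossover is handled. Either use the period-1 comparison at 3 months, or a crossover mixed model on the 3- and 6-month values with treatment, period and sequence terms. Adjust for baseline in either case.
- **G2:** report changes from baseline within a group, overall and by sex, as descriptive and not as evidence of a Care4AD effect.

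The cost is wording in two sections, with no new data or visits. The sponsor gives up the easier within-group claim.

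### Primary endpoint 3 (functional change over 6 months) names no treatment comparison although everyone switches condition at 3 months, and G2 gives function no treatment-effect model

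*Combined protocol and SAP*

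**What the plan says.** G1 states that the Phase II sample size of 100 was calculated on three primary endpoints. The first concerns caregiver burden in the Intervention group. The second and third are "better adherence in the Intervention group compared to control group, and 3) change in functional performance over 6 month". The third refers to no group and names no instrument.

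F1 (Study 2) describes a 1:1 randomised 6-month crossover and says: "At the 3 month visit, participants will be crossed over to either intervention or control and follow procedures". F2, under the 3-month visit, confirms that "intervention group will become controls and controls will become part of the intervention group". Neither section describes a washout.

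In G2 (Study 2), the main linear mixed model tests the intervention effect on "caregiver burden/stress at 6 months compared to baseline and between groups". Further mixed models or GEEs cover the "secondary outcomes (depression, cognitive function, QoL, fear of falls, neurotic tendency including fatigue, physical activity, adverse events, missing appointments". Motor measures enter the regressions only as "baseline motor variables (e.g., balance and gait speed". Functional performance, with gait speed as the example, appears once more, in a Spearman correlation. The Katz and Lawton scales appear in an agreement analysis.

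For physical activity, F2 says in one place: "Subjects will be monitored for up to 1 week continuously at baseline and at the end of the study". Its 3-month list also includes the measure: "Questionnaires, Gait, Balance, Motor-Cognitive Exercise program, Spontaneous physical activity monitoring, Upper Extremity Test, Photos and Media".

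**The concern.** By month 6 every participant has spent about three months in each condition. A change from baseline to month 6 then has no concurrent control. It contains part of any Care4AD effect, together with whatever disease progression, practice or seasonal change occurs over the same period. In people with memory loss, a decline over six months is plausible and could mask a benefit. Improvement through practice could equally be taken for one.

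G2 does not repair this, because it applies no treatment model to the endpoint. The one visit it names for a treatment effect, and that for burden, is month 6, after the switch. A primary endpoint could therefore be reported exactly as G1 words it and say nothing about the intervention.

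**Working it through.** **The plan's own figure.** N = 100 cannot be reproduced, because G1 gives no effect size, SD, power or dropout for any endpoint. As a back-calculation only, a simple parallel comparison with 50 per group (two-sided 0.05; G2 does not state sidedness) detects 2.80 × √(2/50) = 0.56 SD at an assumed 80% power.

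**What each contrast estimates.** Let t be the Care4AD effect after 3 months, c the share of it that persists 3 months after switching off (0 to 1, same direction), and p the change from baseline to 6 months that would occur anyway. Mean changes from baseline, leaving out the common 3-month shift, are:

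| Sequence | 3 months | 6 months |
|---|---|---|
| Care4AD first | t | p + ct |
| Control first | 0 | p + t |

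From these:

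- Average within-person 6-month change: p + t(1+c)/2
- 6-month difference, groups as randomised: ct − t = −(1−c)t
- 6-month difference, groups by current condition: +(1−c)t
- Crossover estimate (half the sequence difference in 3-month minus 6-month values): [(t − ct) + t]/2 = t(1 − c/2)
- 3-month difference: t

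Only the within-person change contains p. The 6-month contrast equals t only if c = 0 and groups are labelled by current condition.

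**Illustration.** Assume t = 0.40 SD; the documents give no value.

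| c | Decline p that cancels the within-person change | Size of 6-month contrast | Crossover estimate | 3-month contrast |
|---|---|---|---|---|
| 0 | 0.20 | 0.40 | 0.40 | 0.40 |
| 0.5 | 0.30 | 0.20 | 0.30 | 0.40 |
| 1 | 0.40 | 0 | 0.20 | 0.40 |

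**Precision of the two usable contrasts.** Assume correlation r = 0.7 between visits, 50 analysed per sequence, two-sided 0.05 and 80% power.

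- Crossover SE = √(2(1−0.7)) × √(2/50)/2 = 0.0775. Detectable t = 2.80 × 0.0775/(1−c/2) = 0.22, 0.25, 0.29, 0.35 and 0.43 SD for c = 0, 0.25, 0.5, 0.75 and 1.
- 3-month baseline-adjusted SE = √(1−0.49) × √(2/50) = 0.1428. Detectable t = 0.40 SD at any c.
- Equal power at c = 2(1 − 1/√(2(1+r))) = 0.91 (0.85 at r = 0.5, 0.95 at r = 0.8).
- With 40 analysed per sequence: crossover 0.24 SD (c = 0) or 0.32 SD (c = 0.5); 3-month contrast 0.45 SD.

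The crossover model is thus the more precise unless carryover is nearly complete, but it underestimates t by 12.5%, 25% or 50% at c = 0.25, 0.5 or 1. The 3-month contrast has no such bias. Each covers the other's weakness.

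**The case against.** **The endpoint may be loosely worded rather than wrong.** The six months could simply be the trial's length. G2 also says that mixed models can test group differences over time and at particular visits. This makes the gap partly one of specification, and the needed data are scheduled. But G2 states this as a general property, does not apply the models to function, and names no current-treatment or period term.

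**Some function is modelled.** Physical activity, which F2 describes in terms of daily mobility, and cognitive function are both on G2's treatment-effect list. That is correct, so it would be too broad to say that nothing functional is tested. Both are secondary, however, and neither is identified with endpoint 3.

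**Function may be a stray primary endpoint.** Section D's Phase II aims are care coordination, adherence and caregiver burden, and F1 calls the design a pilot. This stands, and it makes demotion a reasonable alternative.

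**A stronger reading is tempting but unsupported.** A reader might infer that the trial is likely to show a significant harmful effect at 6 months. Under t = 0.40 SD, r = 0.7, c = 0 and as-randomised labels, the chance of significance in the wrong direction is Φ(0.40/0.1428 − 1.96) = 80%. But 0.40 SD is itself the effect detectable with 80% power at that SE, so the figure follows by construction. It falls to 29% at t = 0.20, 10% at t = 0.10, and 64% at t = 0.40 with r = 0.5. It also needs as-randomised labels at month 6, whereas F2 says the groups exchange roles. By current condition the contrast has the right sign and is only diluted. The documents do not settle which labels apply.

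**Visits.** Section I says the intervention group needs no clinic visit after baseline, which sits awkwardly with F2's schedule. Whether both groups are assessed in the same setting needs confirming.

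**Conclusion.** The point holds and should be corrected. As worded, a baseline-to-6-month change cannot separate a Care4AD effect from change over time, and no treatment model is assigned to gait, balance or functional performance. This follows from the switch alone and needs no assumed effect size.

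The loss depends on unknowns. Within-person change is off by the whole of p, and a 6-month contrast by the factor (1−c) and possibly by sign. These expressions assume carryover between 0 and 1 in the direction of the effect. All SD figures, power figures and wrong-direction percentages illustrate assumed t and r and are not properties of this trial. Nor can one conclude that the trial is incapable of assessing function: F2 schedules gait, balance and the upper-extremity test at baseline, 3 and 6 months, so a randomised contrast is available once it is specified.

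**What to change.** 1. Define endpoint 3 as the difference in one named functional measure, such as habitual gait speed, between Care4AD and control conditions.
2. Analyse the 3- and 6-month values in a mixed model with current treatment and period, adjusted for baseline. Report the baseline-adjusted 3-month between-arm contrast beside it as the carryover-free estimate.
3. State that no treatment conclusion will be drawn from within-person 6-month change.
4. Alternatively, since Section D does not list function among its aims, move it to secondary with the same analysis. This also leaves one fewer primary endpoint tested at 0.05.
5. Keep the 3-month physical activity recording in F2's visit list and correct the monitoring paragraph to match. Otherwise the only pre-switch comparison for that outcome is lost.

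The cost is wording and minor analysis work. No visits, procedures or participants are added if F2's schedule is followed in both groups. The drawback is that the 3-month contrast is usually less precise than the crossover model, which is why it accompanies the model and does not replace it.

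Separately, the exercise programme listed at the 3-month visit and the exercise metrics in the Spearman analysis match no procedure described for either arm. The sponsor should clarify whether they are leftover text or a real component. The main finding does not depend on them.
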